10.6.2 Laboratory Test Results

Shifts tables of the most extreme post-baseline (after the first IP in 20130255 study) laboratory toxicity based on CTCAE grade relative to 20130255 study baseline will be tabulated by treatment group. Laboratory values and changes from 20130255 study baseline for selected panels may be summarized descriptively by visit and treatment group. In the cases when CTCAE grading scales include numeric ranges in combination with clinical assessment (eg, potassium [hypokalemia]), laboratory test results may be summarized based on standard normal ranges or by CTCAE grade utilizing investigator's input.

Shifts tables of the laboratory toxicity for **absolute neutrophil count (ANC)** based on CTCAE grade relative to baseline will be tabulated by treatment group.

Summary of change from baseline for ANC, alanine aminotransferase (ALT) and aspartate aminotransferase (AST) will also be provided by visit.

Subject incidence of liver function test abnormalities, including AST, ALT, Total Bilirubin (TBL) and Alkaline Phosphatase (ALP), will also be summarized by treatment group.

10.6.3 Vital Signs

The analyses of vital signs (systolic and diastolic blood pressure and heart rate) will include summary statistics of change from baseline over time by treatment group. Systolic and diastolic blood pressure will also be analyzed by change from baseline in categories: ≥ 10 , < 20 mmHg and ≥ 20 mmHg and analyzed for SBP >140 mmHg (Yes vs. No) and DBP > 90 mmHg (Yes vs. No) at each time point.

10.6.4 Columbia-Suicide Severity Rating Scale (C-SSRS)

No statistical testing will be performed on C-SSRS. The number and percentage of subjects reporting any suicidal ideation and any suicidal behavior will be summarized descriptively by treatment group and visit. **Shift table of C-SSRS maximum severity of suicidal ideation/behavior compared to baseline will be provided by treatment group.**

10.6.5 Electrocardiogram (ECG)

The ECG measurements from this clinical study were performed as per standard of care for routine safety monitoring, rather than for purposes of assessment of potential QTc effect. Because these evaluations may not necessarily be performed under the rigorous conditions expected to lead to meaningful evaluation of QTc data; neither summaries nor statistical analyses will be provided, and these data would not be expected to be useful for meta-analysis with data from other trials. **A summary of ECG diagnoses will be tabulated.**

10.6.6 Antibody Formation

The number and percentage of subjects who develop anti-AMG 334 antibodies (binding and, if positive, neutralizing) for baseline and post-baseline will be tabulated by treatment group. **The list of subjects testing positive for antibodies at any time will be provided.**

10.6.7 Exposure to Investigational Product

Descriptive statistics will be produced to describe the exposure to investigational product by treatment group. The number and percentage of subjects with dose change, reason for dose change and duration of exposure to investigational product in days will be summarized by treatment group.

10.6.8 Exposure to Concomitant Medication

The number and proportion of subjects receiving headache-related medication will be summarized **by acute medication category** for each treatment group.

10.7 Pharmacokinetic or Pharmacokinetic/Pharmacodynamic Analysis

The pharmacokinetic concentration will be summarized with descriptive statistics by visit and treatment group using PK analyses set. Treatment group assignments will follow those specified for the efficacy analysis.

11. Changes From Protocol-specified Analyses

Since most subjects are likely to receive both 70 mg and 140 mg in this study, descriptive summaries on efficacy endpoints will be presented by randomized treatment group in the 20120295 parent study and first dose received in this study, and not by maximum dose as described in the protocol.

Bed days and missed work/school days due to migraine symptoms not summarized since they were not summarized in 20120295 parent study.

12. Literature Citations / References

Fairclough DL1, Cella DF. Functional Assessment of Cancer Therapy (FACT G): non-response to individual questions. Qual Life Res. 1996 Jun;5(3):321-9.

13. Prioritization of Analyses

Summary tables of safety and efficacy will be produced for the use of the annual report and to support publications, if warranted. Therefore, they might be prepared earlier than others.

14. Data Not Covered by This Plan

There are no plans to specifically analyze or summarize the following data points. However, a listing of these data may be presented and/or additional exploratory analyses may be performed should inspection of the data warrant.

- ECG data
- general comments
- population pharmacokinetics
- biomarker

15. Appendices

[figure not shown]
Appendix A. Reference Values/Toxicity Grades

Adverse event severity and laboratory toxicity are graded based on NCI Common Toxicity Criteria version 4 or higher, which is available at the following:

http://evs.nci.nih.gov/ftp1/CTCAE/CTCAE_4.03_2010-06-14_QuickReference_5x7.pdf

CCI

CCI

CCI

CCI

CCI

CCI

CCI

CCI

CCI

CCI

CCI

CCI

Appendix C. Calculation of eDiary Efficacy Endpoints

Calendar-Day-Headache

Every headache (HA) event reported is identified by a unique headache event number.

If a patient responds NO to the question “HA ended while sleeping” in their eDiary then the HA end date-time is defined as the HA end date-time. If a patient responds YES to the question “HA ended while sleeping” in their eDiary then HA end date-time is defined as the wake up date-time.

For each HA whose start and end date-times are not on the same calendar day, so there are one or more midnights (00:00 AM) between the HA start and end date-times, the headache will be split into a consecutive sequence of calendar-day-headaches using the intervening midnights as end and start date-times. For example, if a head starts on May 5 at 08:00 and ends May 7th 13:00 then this headache will be split into 3 consecutive calendar-day-headaches using midnights of May 6th and May 7th, namely from 05May 08:00 to 06May 00:00, 06May 00:00 to 07May 00:00 and 07 May 00:00 to 07May 13:00, respectively.

For the headache whose start and end date-times are on the same calendar day the corresponding calendar-day-headache is that calendar day.

Each calendar-day-headache has a corresponding duration given by:

- calendar-day-headache duration = HA end date-time – HA start date-time.

The calendar-day-headaches will be sorted by headache start date-time in ascending order.

Calendar-Day-Migraine-Headache

A calendar-day-headache is a calendar-day-migraine-headache, if

- it is a migraine without aura, ie, the calendar-day-headache duration is ≥ 4 hours and meet the following criteria a and/or b:
 - a) ≥ 2 of the following pain features:
 - Unilateral
 - Throbbing
 - Moderate to severe
 - Exacerbated with exercise/physical activity

b) ≥ 1 of the associated symptoms:

- Nausea and/or vomiting
- Photophobia and phonophobia

OR

➤ It is a migraine with aura, ie, meet the following criteria c and d:

c) Meeting ≥ 1 of the following fully reversible aura symptoms:

- Visual
- Sensory
- Speech and/or language
- Retinal
- Brainstem

d) Aura is accompanied or followed within 60 minutes by a calendar-day-headache duration ≥ 4 hours.

OR

➤ If a migraine specific medication (triptan or ergot-derivatives) is taken on the same calendar day (date) as a calendar-day-headache start date and the time in which this migraine specific medication is taken is less than or equal to the calendar-day-headache start time, regardless of calendar-day-headache duration.

Migraine Day

A calendar day is called a migraine day if

➤ there is at least one calendar-day-migraine-headache on that day

OR

➤ the subject took a migraine specific medication (triptan or ergot-derivatives) on that calendar day regardless of

- whether the subject had or not had a calendar-day-headache
- the duration and pain features or associated symptoms, if the medication was used to treat headache pain

“Aura is accompanied” means either aura start or end date-time is between the start date-time and end date-time of a calendar-day-headache, or aura start date time is before calendar-day-headache start date time and aura end date time is after calendar-day-headache end date time. “Aura is followed within 60 minutes” means the difference of a calendar-day-headache start date time minus aura end date time is between 0 and 60 minutes.

Or use the following algorithm:

The calendar-day-headache start date time is before the aura start date time and the calendar-day-headache end date time is after the aura start date time, or the calendar-day-headache start date time is between the aura start date time and ≤ 0 minutes after the aura end date time.

The calendar-day-headaches and the symptoms are matched by headache event number ID first, then by date (to match calendar-day-headaches, from a long headache spans several calendar days with same ID, with daily symptom records).

If there are two sets of symptoms associated with one headache that begin and end on the same day, the set of symptoms whose eDiary date matches the headache's beginning date will be used.

Headache Day

Any calendar day in which the subject experiences a qualified migraine or non-migraine headache (initial onset, continuation or recurrence of the headache).

A calendar day is a headache day if

- there is at least one calendar-day-headache on that calendar day
 - with calendar-day-headache duration ≥ 4 hours

OR

- with any duration for which acute medication (simple analgesics, combination analgesics, triptans, ergot-derivatives, opiates) was administered for treatment of headache pain

OR

- The calendar day is a migraine day (to cover the additional case: the subject took a migraine specific medication (triptan or ergot-derivatives) on that calendar day even without any calendar-day-headache).

Qualified Headache

- a qualified migraine headache (including an aura-only event that is treated with acute migraine-specific medication), or
- a qualified non-migraine headache, which is a headache that lasts continuously for ≥ 4 hours and is not a qualified migraine headache, or
- a headache of any duration for which acute headache treatment is administered

Acute Medication Use Day

An acute medication use day is any calendar day on which a subject uses acute medications. Medications for acute treatment of migraine pain include simple analgesics, combination analgesics, triptans, ergot derivatives and opiates. More specifically, acute medications include triptan-based migraine medications, non-opioid acute headache medications, ergotamine-based migraine medications, opioid-containing acute headache medications, opioid-containing butalbital containing medications and non-opioid butalbital containing medications (medication code is not missing nor equal to “999999”).

Migraine Specific Medication Use Day

A migraine specific medication use day is any calendar day on which a subject uses migraine-specific medication (triptan or ergot-derivatives). Migraine specific medication use day is based on the date-time migraine-specific medication is taken.

eDiary Day

An eDiary day is any calendar day on which a subject has recorded eDiary data. An eDiary day can be identified by the availability of eDiary date-time information for that day such as whether a headache starts and/or ends on that day, the subject woke up on that day while a headache ends during sleep or aura start. An eDiary is also any day on which medication use start date-time is recorded even if no headache is recorded on that day.

Information Day (used for Headache Day calculations)

An information day is any calendar day which is either an eDiary or headache day.

Migraine Attack

A migraine attack is an episode of any qualified migraine headache or episode for which the subject took a triptan or ergot-derivative to treat headache or aura. The following rules will be used for distinguishing an attack of long duration from two attacks, or for distinguishing between attacks and relapses:

- A migraine attack which is interrupted by sleep or temporarily remits, and then recurs within 48 hours after onset of the attack will be considered as one attack, and not two.
- An attack primarily treated successfully with medication but with relapse within 48 hours will be considered as one attack.

Monthly Cumulative Migraine Headache Duration (in hour)

Repeat the step for baseline phase and each 28-day interval:

Add up durations for all calendar-day-migraine-headaches in baseline phase or each 28-day interval after Day 1.

Extent of Exposure and Exposure Adjusted Data Presentation

Subjects are allocated into three groups for non-AE safety data presentation:

- 80% of time exposed to 70 mg
- 80% of time exposed to 140 mg
- remaining subjects

Subjects are allocated to treatment groups based on the relative timing a subject increases dose to 140 mg based on when 20130255 Protocol Amendment 3 was implemented with respect to the subjects study start date (see [Section 6.6](#)).

The calculation is reasonable given low incidence of dose withholding and dose administration error.

In the extent of exposure summary table

- Total number of injection is calculated based on actual dose administered. Dose withholding is counted. Dose administration error is not counted. For example, during the 140 mg treatment period, if a subject only received 70 mg for one visit, this administration is still counted in 140 mg dose group.
- Exposure duration is calculated based on total duration, as discussed above.

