10.1.1.4 Clinical Outcome Assessments - Definition of Terms Included in Endpoints

Clinical outcome assessments will be determined via diary data.

- Migraine Day: Any calendar day in which the subject experiences a qualified migraine headache (onset, continuation, or recurrence of the migraine headache). A qualified migraine headache is defined either as a migraine without aura or a migraine with aura as outlined below:
 1. A migraine without aura, lasting for ≥ 4 continuous hours, and meeting criteria a and/or b:
 - a) ≥ 2 of the following pain features:
 - Unilateral
 - Throbbing
 - Moderate to severe
 - Exacerbated with exercise/physical activity
 - b) ≥ 1 of the associated symptoms:
 - Nausea and/or vomiting
 - Photophobia and phonophobia

OR

2. A migraine with aura and meeting criteria a and b:
 - a) Meeting ≥ 1 of the following fully reversible aura symptoms:
 - Visual
 - Sensory
 - Speech and/or language
 - Retinal
 - Brainstem
 - b) Aura is accompanied, or followed within 60 minutes, by headache lasting for ≥ 4 continuous hours

If the subject took a triptan or ergot-derivative on a calendar day, then it will be counted as a migraine day regardless of the duration and pain features/associated symptoms.

- Headache Day: Any calendar day in which the subject experiences a qualified migraine or non-migraine headache (initial onset, continuation or recurrence of the headache lasting ≥ 4 continuous hours, or a headache of any duration for which acute medication was administered (Refer to [Section 6.4](#)) for treatment of headache pain.

- Headache Day with moderate or severe intensity: Any calendar day in which the subject experiences a headache, with headache pain lasting ≥ 4 continuous hours, and a peak severity of moderate to severe, or of any severity or duration if the subject takes a triptan or ergot-derivative for headache pain
- Monthly Migraine Days: Number of migraine days in any 28-consecutive day interval relative to study day 1. See above for the definition of a migraine day.
- Monthly Headache Days: Number of headache days in any 28-consecutive day interval relative to study day 1. See above for the definition of a headache day.
- Migraine Attack: An episode of any qualified migraine headache or episode for which the subject took a triptan or ergot-derivative to treat headache or aura. The following rules will be used for distinguishing an attack of long duration from two attacks, or for distinguishing between attacks and relapses:

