6.1.2 Efficacy Endpoints

eDiary Day

Day in which a subject uses the eDiary.

Migraine Day

A migraine day is any calendar day in which the subject experiences a qualified migraine headache. A qualified migraine headache is defined either as a migraine with or without aura as outlined below:

1. A migraine without aura is defined as a headache lasting continuously for ≥ 4 hours, and meeting criteria a and/or b:
 - a) ≥ 2 of the following pain features:
 - Unilateral
 - Throbbing
 - Moderate to severe
 - Exacerbated with exercise/physical activity
 - b) ≥ 1 of the associated symptoms:
 - Nausea and/or vomiting
 - Photophobia and phonophobia

OR

2. A migraine with aura and meeting criteria c and d:
 - c) The occurrence of ≥ 1 of the following fully reversible aura symptoms:
 - Visual
 - Sensory
 - Speech and/or language
 - Retinal
 - Brainstem
 - d) Aura is accompanied, or followed within 60 minutes, by headache lasting continuously for ≥ 4 continuous hours (see [Appendix C](#)).

If the subject took a triptan or ergot-derivative during aura or to treat headache on a calendar day, then it will be counted as a migraine day regardless of the duration and pain features or associated symptoms.

Monthly Migraine Days

Monthly migraine days is the number of migraine days **between each monthly IP dose normalized to 28 day equivalents**, relative to study day 1 in the first 3 months, between the month 5 and 6 visit, between the month 9 and 10 visit and **between the month 12 and 13 visit**. Hereafter, the corresponding visits for these intervals will be reported/presented as/referred to month 1, month 2, month 3, month 6, month 10 and

month 13 visit, respectively. All available eDiary data for the visits will be used and prorated to 28-day equivalents.

Qualified Headache

A migraine or non-migraine headache which lasts ≥ 4 continuous hours, or a headache of any duration for which acute medication was administered for treatment of headache.

In particular, a qualified headache is:

- a qualified migraine headache (including an aura-only event that is treated with acute migraine-specific medication), or
- a qualified non-migraine headache, which is a headache that lasts continuously for ≥ 4 hours and is not a qualified migraine headache, or
- a headache of any duration for which acute medication is administered.

Headache Day

Any calendar day in which the subject experiences a qualified migraine or non-migraine headache.

Monthly Headache Days

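### SAP Appendix C applies the 4-hour test to midnight-split pieces of a headache; the protocol and SAP 6.1.2 apply it to the continuous headache, and SAP Section 11 does not list the departure

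*SAP*

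**What the plan says.** Protocol 10.1.1.4 requires a qualifying migraine to last at least 4 continuous hours. It then defines a migraine day as "Any calendar day in which the subject experiences a qualified migraine headache (onset, continuation, or recurrence of the migraine headache"). SAP 6.1.2 keeps the test on the headache: "A migraine without aura is defined as a headache lasting continuously for ≥ 4 hours, and meeting criteria a and/or b". For aura it requires that the aura be accompanied or followed "by headache lasting continuously for ≥ 4 continuous hours". That aura criterion is the only place in the migraine-day definition that points to Appendix C.

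Appendix C works differently. For a headache that crosses midnight, "the headache will be split into a consecutive sequence of calendar-day-headaches using the intervening midnights as end and start date-times". The duration is given as "calendar-day-headache duration = HA end date-time – HA start date-time". The 4-hour requirement then falls on the piece in three places:

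- migraine without aura: "it is a migraine without aura, ie, the calendar-day-headache duration is ≥ 4 hours and meet the following criteria a and/or b";
- migraine with aura: "Aura is accompanied or followed within 60 minutes by a calendar-day-headache duration ≥ 4 hours";
- the operative bullet for a headache day.

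No clause carries qualification from the whole headache over to its pieces. Two other parts of Appendix C do not match the piece test: the opening sentence of the headache-day definition, which still counts continuation, and the qualified-headache definition, which still tests the continuous headache.

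A triptan or ergot taken on a day makes it a migraine day whatever the duration. If a headache ended during sleep, "HA end date-time is defined as the wake up date-time".

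SAP Section 11 lists two changes from the protocol: the treatment grouping for efficacy summaries, and the omission of bed days and missed work or school days.

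**The concern.** Splitting at midnight is a sensible way to allocate hours to days. Using the pieces to decide whether a headache qualifies is another matter, because it makes the count depend on clock time. Two identical migraines can score differently only because one starts in the evening. A day is lost wherever a piece is shorter than 4 hours and nothing else covers that day. For migraine days, cover means a triptan or ergot, or another qualifying headache. For headache days, any acute medication given for the headache also counts.

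Two secondary endpoints, monthly migraine days and 50% response, rest directly on this count, as do headache days (exploratory). The migraine hours in Appendix C are summed over the same qualifying pieces, so they follow the same rule. The study tests no hypotheses, so these descriptive counts are the efficacy result. A reader who takes the definition from the protocol or from SAP 6.1.2 would misread what was counted.

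**Working it through.** **Step 1: the SAP's own example.** A headache from 5 May 08:00 to 7 May 13:00 splits into 16 + 24 + 13 = 53 h, which is 3 pieces, as the SAP states. Every piece is at least 4 h, so both rules give 3 days. The example cannot show the conflict.

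**Step 2: headaches with a short piece.** Symptom criteria are taken as met, with no triptan or ergot and no other headache on those days. Whole-event rule: if the headache lasts at least 4 h, every day it touches counts. Piece rule: only pieces of at least 4 h count.

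| Headache | Pieces (h) | Whole-event days | Piece-rule days |
|---|---|---|---|
| 20:30 to 03:30, not ended in sleep | 3.5 + 3.5 | 2 | 0 |
| 20:30, ended in sleep, woke 07:00 | 3.5 + 7 | 2 | 1 |
| 18:00 to 02:00, not ended in sleep | 6 + 2 | 2 | 1 |
| 21:00 to 03:00 two days later, not ended in sleep | 3 + 24 + 3 | 3 | 1 |

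**Step 3: average loss per headache.** The documents give no onset times or durations, so these are assumptions: onset uniform over 24 h, no overlapping headaches, no covering medication, wake-up rule ignored, duration D of at least 4 h.

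- Days touched: 1 + D/24.
- The first piece is under 4 h if onset is after 20:00: 4/24 = 1/6.
- The last piece is under 4 h if the end is before 04:00: 4/24 = 1/6.
- Days lost: 1/6 + 1/6 = 1/3, whatever D is. Short pieces average 2 h, so 1/3 × 2 = 0.67 h is lost.
- Wake-up rule at its maximum (every headache ending between 00:00 and 07:00 is recorded as ending at 07:00): the last piece is never short, so the loss is 1/6.

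| D (h) | Whole-event days | Piece rule | Change | Piece rule, maximum wake-up | Change |
|---|---|---|---|---|---|
| 6 | 1.25 | 0.917 | -27% | 1.083 | -13% |
| 12 | 1.50 | 1.167 | -22% | 1.333 | -11% |
| 24 | 2.00 | 1.667 | -17% | 1.833 | -8% |
| 72 | 4.00 | 3.667 | -8% | 3.833 | -4% |

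If half of the remaining short-piece days are also covered, the loss in the last column halves to 1/12 day: -7%, -6%, -4% and -2%.

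**Step 4: effect on percent change when the same rule is used throughout.** Take a fall from 12 to 6 headaches of 12 h, with the wake-up rule ignored. The whole-event rule gives 18 to 9 days, -50.0%. If a share c of short-piece days is covered, the piece rule gives 1.5 - (1 - c)/3 days per headache.

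- c stable, for example 0: 12 × 1.167 = 14 to 6 × 1.167 = 7, -50.0%.
- c falls from 50% to 25%: 12 × 1.333 = 16.0 to 6 × 1.25 = 7.5, -53.1%.
- c rises from 25% to 50%: 12 × 1.25 = 15.0 to 6 × 1.333 = 8.0, -46.7%.

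**The case against.** The strongest reply is that the duration formula uses the event-level labels for headache end and start. Read literally, it returns the length of the whole headache, and Appendix C would then agree with the protocol. The formula is loosely worded, but this reading fails. The split makes the midnights the start and end times of the pieces, and Appendix C later adds up piece durations to obtain migraine hours. With whole-event durations, the SAP's own 53 h headache would contribute 3 × 53 = 159 h. If the whole event is nevertheless what is meant, the text needs to say so.

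A second reply is that the algorithm is disclosed in an appendix written for this purpose. That is so, but SAP 6.1.2 points to it only at the aura criterion and states a different test, and Section 11 is where a reader looks for departures.

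A third reply is that the practical effect may be small, and much of this stands. Many midnight-crossing headaches lose nothing. Triptans, ergots and other headaches cover some days, and the wake-up rule protects many pieces after midnight, though not a short evening piece. If one rule is used throughout and both headache duration and coverage are stable, percent change is unaffected. The uniform onset and the coverage shares above are assumptions, not trial data.

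**Conclusion.** The conflict is real and should be fixed. On the better reading of Appendix C, migraine days, 50% response and headache days are not counted as the protocol defines them, and migraine hours follow from the same pieces. The size in this trial is unknown. The illustrative loss of 1/3 day per headache assumes uniform onset, no coverage and no wake-up effect; 1/6 day is the corresponding figure with the wake-up rule at its maximum. The direction of any bias in percent change cannot be stated. The adverse-event primary endpoint is untouched.

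A reader might go further and infer that baseline days were counted on whole headaches and follow-up days on pieces, which would create an apparent improvement. The documents do not support that. Appendix C sums calendar-day migraine headaches in the baseline phase. Those objects exist only after the piece test, and a day containing one is by definition a migraine day. This implies that the piece rule also applies at baseline. What remains is a gap in the wording. The instruction to repeat the calculation for baseline is explicit only for migraine hours, and SAP 6.3 otherwise refers to the baseline as defined in the parent study.

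**What to change.** Preferred: in Appendix C, apply the 4-hour test to the whole headache, identified by its headache event number. Count every calendar day it touches, and use the pieces only to sum hours.

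Alternative, if the piece rule is kept for comparability with the parent study: align SAP 6.1.2 and the headache-day text in Appendix C with it and list it in Section 11. Report migraine days, headache days, 50% response and migraine hours under the protocol rule in one sensitivity table.

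In either case, add two statements:

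- Baseline, parent-study Month 3 and follow-up values all use the same algorithm.
- Which symptom record qualifies a headache that spans several days. Appendix C matches symptoms by event number and then by date, and gives no rule for a whole event whose daily records differ.

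The cost is SAP wording and one extra derivation, with one table if the piece rule is kept. All of it uses existing eDiary data and needs no new collection. The drawback is that baseline values under the protocol rule may differ from those reported in the parent study.

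### SAP Appendix C: as it reads, the alternative aura-headache algorithm drops the 60-minute window that every other statement of the rule allows

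*SAP*

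**What the plan says.** The criterion for migraine with aura is stated in the same way throughout. SAP Section 6.1.2 has "Aura is accompanied, or followed within 60 minutes, by headache" of at least 4 continuous hours. The protocol uses the same 60-minute wording in its glossary (Migraine Day) and in Section 10.1.1.4. In SAP Appendix C, criterion d for a calendar-day-migraine-headache reads "Aura is accompanied or followed within 60 minutes by a calendar-day-headache duration ≥ 4 hours".

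Under Migraine Day, Appendix C then turns this into operational rules. A verbal explanation comes first. It defines what counts as accompanied, and says that being followed within 60 minutes "means the difference of a calendar-day-headache start date time minus aura end date time is between 0 and 60 minutes". The next line is "Or use the following algorithm", and a two-branch algorithm follows:

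- Branch 1: "The calendar-day-headache start date time is before the aura start date time and the calendar-day-headache end date time is after the aura start date time".
- Branch 2: "the calendar-day-headache start date time is between the aura start date time and ≤ 0 minutes after the aura end date time".

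The upper limit in branch 2 is therefore "≤ 0 minutes after the aura end date time". The SAP does not say which version governs or when to use one rather than the other.

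**The concern.** Two specifications of one criterion, offered as interchangeable, should classify every headache alike. As the text reads, these do not. Branch 2 ends at the moment the aura ends. Branch 1 needs the headache to begin before the aura, so it cannot restore the missing hour. A programmer who follows the algorithm loses the followed-by-headache half of the definition.

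Appendix C is the working specification for the eDiary endpoints, so this is an operative derivation rule. Four measures depend on it:

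- monthly migraine days (secondary);
- the 50% response derived from them (secondary);
- cumulative hours (secondary), which SAP Section 6.1.2 and Appendix C build from qualifying migraine headaches;
- migraine attacks (exploratory).

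Headache days do not depend on it, because any headache of at least 4 hours already counts. The primary endpoint, subject incidence of adverse events, is untouched.

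**Working it through.** No sample size or error rate is involved. The check is whether the two rules agree and, where they differ, which days change.

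**Notation.** Aura runs from A1 to A2 and headache from H1 to H2, in minutes. W is the limit after aura end in branch 2.

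- Verbal rule: true if H1 ≤ A1 ≤ H2, or H1 ≤ A2 ≤ H2, or (A1 < H1 and A2 > H2), or 0 ≤ H1 − A2 ≤ 60.
- Algorithm: true if (H1 < A1 and H2 > A1), or A1 ≤ H1 ≤ A2 + W. As the text reads, W = 0.

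**One example.** Aura 08:00 to 08:30, headache 09:00 to 14:00 (5 hours).

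- Verbal rule: H1 − A2 = 30 minutes, and 0 ≤ 30 ≤ 60, so it is met.
- Algorithm, W = 0: branch 1 fails (09:00 is not before 08:00). Branch 2 needs 08:00 ≤ 09:00 ≤ 08:30 and fails. Not met.
- Algorithm, W = 60: branch 2 needs 08:00 ≤ 09:00 ≤ 09:30. Met.

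**Systematic comparison.** I took aura durations of 5 to 120 minutes in steps of 5 (24 values), headache durations of 240 to 720 minutes in steps of 60 (9 values), and 1,100 one-minute onset times: 24 × 9 × 1,100 = 237,600 configurations. Splitting of headaches at midnight was not modelled.

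| Limit W | Verbal yes, algorithm no | Verbal no, algorithm yes |
|---|---|---|
| 60 | 216 | 0 |
| 0 | 13,176 | 0 |

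The 216 (24 × 9 × 1) are a zero-width boundary: the headache ends at the exact minute the aura starts. The other 13,176 − 216 = 12,960 (24 × 9 × 60) are all the cases with onset 1 to 60 minutes after aura end, and nothing else. So with W = 60 the algorithm reproduces the verbal rule apart from that boundary. With W = 0 it only removes cases and adds none. These counts describe the grid, not how often such headaches occur in patients.

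**Which days change status.** A rejected headache of at least 4 hours may still qualify as migraine without aura. It fails that route only if it has at most one of four pain features (1 + 4 = 5 of 16 combinations), no nausea or vomiting (1 of 2), and not both photophobia and phonophobia (3 of 4). That is 5 × 1 × 3 = 15 of 16 × 2 × 4 = 128 combinations, again a count of combinations and not a frequency. The day must also have no triptan or ergot use and no other migraine headache, since either makes it a migraine day anyway. Cumulative hours are summed headache by headache, so another migraine headache on the same day keeps the day but not the lost headache's hours.

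**Effect on change from baseline.** Let b and p be the migraine days lost under W = 0 at baseline and post-baseline.

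- Window 60 at baseline, 0 in the extension: change shifts by −p, so the reduction looks larger.
- Window 0 in both: change shifts by b − p. If b > p, the reduction looks smaller.
- Window 60 in both: no shift.

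The documents do not say which case applies.

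**The case against.** The strongest objection is that the point rests on a single number. The window is 60 minutes everywhere else, including the sentence just before the algorithm. A limit of zero minutes after an event is unnatural wording, and 60 makes the two rules agree. A digit could have been lost when the PDF was read, which would not be an error in the plan. This stands as a caution: the text cannot separate a lost digit from a typing slip. If the printed page shows 60, the point falls away.

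A second objection is that the consequence is narrow. That also stands. Only a residue of days is exposed, the measures are secondary or exploratory, and the SAP tests no hypotheses.

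A reader might go further and infer that change from baseline is biased towards benefit, with the baseline using 60 minutes and the extension using zero. The documents do not support this. SAP Section 6.3 takes the primary baseline as defined in the parent study, whose derivation is not available here. Nothing shows that the two periods were programmed differently, and for cumulative migraine duration Appendix C applies the same step to the baseline phase and to later intervals. With one rule in both periods, the shift could run either way.

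It would also be too strong to say that the protocol itself counts the 60 minutes from aura end. The protocol says only that headache follows within 60 minutes; counting from aura end is the SAP's operational reading.

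**Conclusion.** As the text reads, the alternative algorithm contradicts the definition it is meant to implement, and the SAP leaves the choice between the two open. Subject to a check of the printed page, it is wrong as written. The agreement of the two rules at 60 minutes suggests that 60 was intended.

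The importance is minor. The direction is certain only for the count itself: the algorithm as printed gives the same number of migraine days or fewer. The size cannot be calculated, because the documents do not say how often the residual headaches occur; that it is probably small is a judgement based on how many conditions must coincide. The conclusion assumes that the limit in the original is 0 and that a programmer could follow the alternative rather than the verbal rule.

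**What to change.** Check the source page of Appendix C. If it shows 0, either set the limit in branch 2 to 60 minutes after aura end or delete the alternative algorithm, so that one rule remains. Either change follows the documents' own definition.

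Also confirm in the derivation program that the same window was applied to the parent-study baseline, the parent-study month 3 data and the extension intervals. The cost is one edit in Appendix C and one program check. If the program already uses 60 minutes throughout, no results change.
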